5.3.3 Targeted rebiopsy

Participants in the **reclassified** category will have both a 12-core TRUS biopsy unguided by the results of the MRI and a biopsy targeting the lesion(s) of concern from the scan. The rationale for doing both biopsies is that to compare the MRI findings to the current goldstandard, a non-targeted TRUS biopsy, we need to include this regardless of the MRI findings. Because this biopsy may not capture the lesion noted on the scan, a targeted biopsy will be performed at the same time. The targeted biopsy will be performed according to the practices of the treating institution but will generally consist of conscious sedation with either an MRI-guided biopsy or a TRUS-guided biopsy directed based on images fused to the MRI. The number of cores taken will be at the discretion of the physician performing the biopsy. Standard of care transrectal ultrasound imaging (TRUS) may be augmented with the setup needed for spatial tracking of the TRUS images. The purpose of this is to facilitate research in spatial mapping biopsy samples within the prostate gland, and to aid with correlation of pathology analysis of the samples with TRUS and MRI imaging data. The tracking setup would be enabled by a tracking system consisting of an electromagnetic field transmitter that establishes the coordinate frame for tracking volume, and several sensors. The transmitter would be mounted on an articulated arm to the patient bed. One sensor will be attached to the handle of the TRUS probe before the procedure. The sensor will remain on the handle outside the patient at all times. The second sensor will be attached with the medical tape to the back of the patient. Prior to TRUS imaging, a calibration procedure may be necessary. If needed, such procedure would involve placing the TRUS probe in a water bath and imaging of a phantom, prior to the patient procedure. This component of the biopsy is not anticipated to add any additional risk or toxicity to the protocol.

5.3.4 Pathologic assessment

- 5.3.4.1 All specimens will be formalin fixed and paraffin embedded as per usual clinical care. Pathology will be reviewed by a pathologist with GU expertise for Gleason grade, disease extent, and number of cores positive. Additional features such as perineural invasion and high-grade PIN will be noted though these will not be used to determine continued protocol eligibility. Each of the cores will be labeled for biopsy location at the time of procedure and will be individually reported. Pathology will be reviewed at the treating center. Specimens will also be labeled as to whether they came from the TRUS biopsy or the targeted biopsy
- 5.3.4.2 TRUS Biopsy: Participants will come off study if they no longer meet eligibility criteria following rebiopsy:
 - >3 cores positive for cancer
 - >50% of any single core containing cancer
 - any Gleason >3+3

- 5.3.4.3 Targeted Biopsy: Participants will be considered pathologically reclassified if either of the following criteria are met on the targeted biopsy:
 - Gleason >3+3
 - >7mm of any core involved with cancer

In this situation, using the criteria of number of cores involved with cancer will no longer be comparable across participants as the number of cores sampled will be variable based on the situation.

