5.1 Patient-reported health states

Participants will be asked to complete patient-reported health state questionnaires at enrollment and following the final on-protocol biopsy. The questionnaire that will be provided to participants for self-administration will include the following:

- The Mishel Uncertainty in Illness Scale Community Form for Active Surveillance (MUIS-AS, Appendix A). The MUIS-AS will evaluate uncertainty, anxiety, and distress associated with the patient's cancer diagnosis.
- *The Service Satisfaction Scale for Cancer Care* (SSS-Ca, Appendix B). The SSS-Ca will evaluate the patient's satisfaction with both the process and outcome of their cancer related care.
- The Expanded Prostate Cancer Index Composite Clinical Practice (EPIC-CP, Appendix C). The EPIC-CP is used to evaluate urinary and sexual function following treatment for prostate cancer. This will specifically be useful in order to assess the progression of urinary symptoms

- overtime in these participants who may be required to undergo serial prostate biopsies, endorectal MRI, etc.
- The American Urological Association Symptom Index (AUA SI, Appendix D), which will be used to evaluate overall urinary bother and function

Questionnaires will be given to participants at their enrollment visit and at the end of study visit following biopsy. Participants will be instructed to complete them independently and to return them by mail to the project coordinator.

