5.2.2.1 Images will be reviewed within the radiology department where the scans were obtained as per current protocols and a standard clinical report will be produced. Images will subsequently be analyzed by study radiologists with extensive experience in GU imaging. The images will be evaluated according to the proposed PIRADS scoring system guidelines. This will specifically look at signal intensity on T2 weighted image (with a discrete, homogenous low signal focus being suspicious for tumor). For DCE, both semi-quantitative and quantitative parameters will be evaluated, with particular attention paid to the dynamic enhancement curve type [70]: (type 1, persistent increase; type 2, plateau; and type 3, decline after initial upslope; type 3 being considered the most suspicious for

prostate cancer, particularly in the presence of a focal asymmetric enhancing lesion). Pharmacokinetic modeling, which will produce quantitative indices [such as K^{trans} (forward volume transfer constant) and v_e (fractional extracellular space)], will be incorporated into the analysis. DWI will also be scored according to signal intensity on high b value image (\geq b1000) and values obtained on ADC map. Index lesion size will be measured on T2WI to categorize those \geq or< 1 cm in size. Extracapsular extension (ECE) and seminal vesicle invasion (SVI) will also be evaluated for.

The interpretation of the MRI will place participants into the following categories:

- 1. **Not-reclassified**: any identified abnormality of the MRI is confined to the gland without definitive evidence of ECE or SVI. Additionally, no lesion is greater than 1 cm in size nor do any identifiable lesions have characteristics of high Gleason grade.
- 2. **Reclassified**: Disease appears to be confined to the prostate (no ECE or SVI) but one or more lesions appear either >1 cm in size or have imaging characteristics concerning for higher Gleason grade disease.
- 3. **T3 or N1:** disease appears to be clearly extending outside the prostate and/or into the seminal vesicles or there is evidence of pathologic involvement of lymph nodes.

If the MRI places a subject into the T3/N1 category, they will meet criteria for coming off protocol and will then receive further treatment per their treating physician. If a participant is in either the **not-reclassified** or the **reclassified** categories, they will proceed with the planned biopsy.

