5.6 Criteria for Removal from Study

Participants will be removed from the study when any of the criteria in section 5.3.3 or 5.3.4 applies. Additional criteria for removal from the study:

- Participant withdraws from the study
- The patient proceeds to prostate-cancer directed therapy
- Death from any cause
- General or specific changes in the participant's condition which render them unacceptable for completion of the protocol in the opinion of the treating investigator.
- Intercurrent illness that prevents completion of the protocol
- Investigator discretion

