7. STUDY CALENDAR

	Pre- Study	MRI Visit (2-14 months post initial biopsy)	Final Bx visit (within 3 months of MRI visit)	End of Study Visit (within 60 days of final bx)
Informed consent	X			
History ^a	X			
Pathology review	X ^b		X ^d	
PSA	X ^c			Xe
Concurrent meds	X			
Height and weight	X			
Performance Status	X			
Patient-reported health	X^{f}			X
Adverse event evaluation		X	X	X

- a: biopsy date, clinical T-category, was the subject staged with a CT of the abdomen and pelvis; was the subject staged with a bone scan; ACE-27 Comorbidity index (Appendix E)
- b: DF/HCC pathology review of original biopsy (no. cores taken, no. cores positive for cancer; % involvement for each positive core; Gleason grade for each positive core; presence and grade of tertiary Gleason grade; evidence of extracapsular extension; evidence of perineural invasion)
- c: last PSA level prior to biopsy diagnosing the prostate cancer
- d: DF/HCC pathology review of "random" and targeted biopsy (as needed) (no. cores taken, no. cores positive for cancer; % involvement for each positive core; Gleason grade for each positive core; presence and grade of tertiary Gleason grade; evidence of extracapsular extension; evidence of perineural invasion)
- e: most recent PSA value
- f: MUIS-AS, Appendix A; SSS-Ca, Appendix B; EPIC-CP, Appendix C; AUA SI, Appendix D

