11. STATISTICAL CONSIDERATIONS

11.1 Study Design/Primary Objective

The primary objective is to determine the sensitivity and specificity of Mp-erMRI relative to repeated standard 12-core TRUS biopsy for classifying upgrading of disease extent or Gleason grade in men considering AS. We hypothesize MP-erMRI prior to AS for men with low risk disease can identify men who harbor more extensive or higher risk prostate cancer.

The study will plan to enroll 130 participants who had diagnostic biopsy less than one year prior to enrollment. After enrollment, participants will undergo a MP-erMRI. This will be reviewed and participants will be characterized into 3 groups: "not reclassified" characterized by findings consistent with small, low-Gleason grade organ-confined tumors, "reclassified" characterized by large, higher-Gleason grade organ-confined tumors, and radiographic T3 and or N1 disease. Less than 10% (roughly 10) of participants who belong to group 3 will be taken off study. Those in groups 1 and 2 will proceed within 3 months of the MP-erMRI to a standard 12-core TRUS biopsy.

11.2 Hypothesis assumptions:

Participants in groups 1 and 2 will receive 12 core TRUS re-biopsy within 3 months of undergoing MP-erMRI. TRUS re-biopsy will be assumed as the gold standard for determining tumor size and grade.

11.2.1 Null hypothesis:

	TRUS Re-biop		
MP-erMRI Results	No Disease Upgrade	Disease Upgrade	Total
Not Reclassified	72	9	81
Reclassified	18 (20%)	21 (70%)	39
Total	90	30	120

11.2.2 Alternative hypothesis:

	TRUS Re-biog		
MP-erMRI Results	No Disease Upgrade	Disease Upgrade	Total
Not Reclassified	85	3	88
Reclassified	5 (6%)	27 (90%)	32
Total	90	30	120

11.3 Power and sample size calculation:

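### Section 11.6 plans no within-man change in questionnaire scores, and about 10 of 130 men (T3/N1 on MRI) have a baseline form but no scheduled follow-up form

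*Combined protocol and SAP*

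**What the plan says.** **Timing of the forms.** Section 5.1: "Questionnaires will be given to participants at their enrollment visit and at the end of study visit following biopsy". The calendar in Section 7 marks the questionnaires at the pre-study visit and at one later column, "End of Study Visit (within 60 days of final bx"). Section 5.5 times that last visit from the same biopsy.

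**T3/N1 men.** Section 5.2.2: "If the MRI places a subject into the T3/N1 category, they will meet criteria for coming off protocol". Section 5 sends only MRI groups 1 and 2 on to rebiopsy. Section 11.1 gives the expected number: "Less than 10% (roughly 10) of participants who belong to group 3 will be taken off study".

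**Men upgraded on rebiopsy.** Section 5.3.4.2: "Participants will come off study if they no longer meet eligibility criteria following rebiopsy". Section 5.6: "Participants will be removed from the study when any of the criteria in section 5.3.3 or 5.3.4 applies". A further trigger in Section 5.6 is "The patient proceeds to prostate-cancer directed therapy". None of these mentions the end of study visit or the questionnaire. Section 5, straight after dealing with pathologically reclassified men, has every participant leave the study only once that visit is over.

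**Objective and analysis.** Section 11.5 sets a secondary objective about the effect of MRI and rebiopsy together on patient-reported health. Section 11.6 gives each answered questionnaire a score and summarises scores by median and interquartile range. It names no change score and no count of missing forms.

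**The concern.** An effect on health states in a single-arm study is a change from before to after. Two separate medians do not measure it. The same pair of medians can arise if no man changes, or if reassured men improve while upgraded men worsen by as much. Within-man change would show the difference.

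The two medians would also come from different men. T3/N1 men answer at enrolment and then have no biopsy date from which a follow-up form could be timed. They are absent from follow-up because of their MRI result, so the absence is not random with respect to what the study measures. The removal wording in 5.3.4.2 and 5.6 could widen the gap if a site acted on it before the end of study visit. At stake is the reading of one descriptive secondary objective.

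**Working it through.** **Inputs**
- Planned enrolment: 130 (11.1).
- T3/N1 men taken off after MRI: roughly 10 (11.1).
- Share upgraded on TRUS rebiopsy: 25% (11.3).
- Other dropout and unreturned forms: not given. Taken as 0 here.

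**Step 1. The plan's own counts.** 130 − 10 = 120 men biopsied, and 25% × 120 = 30 upgraded. Both match the totals of the tables in 11.2. 10/130 = 7.7%, consistent with the stated ceiling of 10%.

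**Step 2. Who has which form, with Section 5 governing**

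| | Baseline form | Follow-up form scheduled |
|---|---|---|
| T3/N1 on MRI | 10 | 0 |
| TRUS-upgraded | 30 | 30 |
| Not upgraded | 90 | 90 |
| Total | 130 | 120 |

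**Step 3. Case mix of the two summaries.** Count T3/N1 or TRUS upgrade as an adverse result.
- Baseline: (10 + 30)/130 = 40/130 = 30.8%.
- Follow-up: 30/120 = 25.0%.

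**Step 4. How far case mix alone can move the median.** Suppose no man's score changes and all forms come back. The baseline median lies between ranks 65 and 66 of 130. If the 10 absent men had the 10 lowest scores, the follow-up median would lie between baseline ranks 70 and 71. If they had the 10 highest, it would lie between ranks 60 and 61. The largest shift is therefore 5 ranks either way (5/130 = 3.8% of the men). The documents do not show which direction applies.

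**Step 5. The removal wording, side by side.** Sections 5 and 5.5: participants stay to the end of study visit. Sections 5.3.4.2 and 5.6: men leave when the biopsy criteria apply, with no timing given. If the second pair were applied first, at least the 30 expected TRUS-upgraded men would have no follow-up form, in addition to the 10. The documents give no figure for men who start therapy before the visit.

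**Step 6. The cross-reference.** Section 5.6 points to 5.3.3 for removal criteria. Section 5.3.3 describes the targeted biopsy and its tracking equipment and contains no removal criterion.

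**The case against.** The strongest reply is that the T3/N1 gap follows from the design. The objective concerns MRI and rebiopsy together, and men without an on-protocol rebiopsy cannot inform it. That stands. It makes sending these men a form optional, since it would answer a different question (MRI alone). It does not justify leaving them in the baseline summary when the follow-up summary lacks them.

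It is also fair that Section 11.6 specifies no before/after contrast, and does not say outright that T3/N1 men enter the baseline summary. But it scores each questionnaire answered and excludes nobody, and the objective is worded as an effect, so readers will compare the two medians.

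On removal, Section 5 largely settles the matter, because its sentence covering all participants follows directly on pathologically reclassified men. What remains is a conflict of wording, plus silence on men who start therapy early.

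Three stronger readings are tempting and are not supported:
- *A reader might infer that up to 40 of 130 men lose their follow-up form.* This requires 5.3.4.2 and 5.6 to override Section 5. Even then 40 is no upper bound, because 5.6 points to all of 5.3.4, including the targeted-biopsy criteria in 5.3.4.3. The 11.2 tables show 5 to 18 MRI-reclassified men without TRUS upgrade. If all of them met those criteria (an assumption), the loss would be 45 to 58 of 130 (34.6% to 44.6%).
- *A reader might infer that the results will be biased in a known direction.* Nothing in the documents establishes one.
- *A reader might infer that the MUIS-AS will be totalled with positive and negative emotions left in the same direction.* The plan states no summing rule at all. The supportable comment is only that its scoring is unstated.

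**Conclusion.** The point holds as a modest one. The planned summary does not match an objective about effect, and about 10 of 130 men (7.7%) would sit in the baseline summary with no scheduled counterpart at follow-up. Adverse results fall from 30.8% to 25.0% of the men summarised. With Section 5 governing and full return of forms, this alone can move the median by at most 5 ranks, so the larger gain from pairing is that it shows change within men.

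This rests on the plan's own expected counts, on no other loss, and on T3/N1 men being included at baseline. The conflict between 5.3.4.2/5.6 and 5/5.5 needs reconciling, but should not be read as a plan to drop upgraded men. The primary sensitivity and specificity analysis uses MRI category and TRUS result, not questionnaires, and is unaffected.

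**What to change.** 1. **Section 11.6.** Make within-man change the patient-reported analysis: median change and interquartile range among men with both forms, optionally with a confidence interval. Report the number of missing follow-up forms by MRI category and by upgrade status. Pairing removes the case-mix difference. The counts show how much is still unobserved.
2. **Sections 5.3.4.2 and 5.6.** Reconcile them with Sections 5 and 5.5 so that coming off study because of the biopsy result, or because therapy has started, does not end collection of the end-of-study questionnaire. This concerns data collection only and leaves clinical management as it is.
3. **Section 5.6.** Correct the pointer to 5.3.3.
4. **Optional.** Send T3/N1 men a form after the MRI and report them separately, as MRI without rebiopsy.

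The cost is a few sentences and a little descriptive analysis. Section 5.1 already says "Participants will be instructed to complete them independently and to return them by mail to the project coordinator", so item 2 needs no extra visit. Item 4, if wanted, adds about 10 forms.

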5.4 PSA

During the time that participants are on study, a PSA will be drawn as per the treating physician (typically every 3-6 months). A change in PSA will not be a criterion for discontinuation of this protocol though may be used clinically to change management at the discretion of the treating physician.

5.5 Duration of Follow Up/End of Study Visit

Participants will also be followed until their final study visit which will occur up to 60 days after the final biopsy.

5.6 Criteria for Removal from Study

Participants will be removed from the study when any of the criteria in section 5.3.3 or 5.3.4 applies. Additional criteria for removal from the study:

- Participant withdraws from the study
- The patient proceeds to prostate-cancer directed therapy
- Death from any cause
- General or specific changes in the participant's condition which render them unacceptable for completion of the protocol in the opinion of the treating investigator.
- Intercurrent illness that prevents completion of the protocol
- Investigator discretion

6. EXPECTED TOXICITIES AND DOSING DELAYS/DOSE MODIFICATIONS

Toxicity assessments will be done using CTEP Version 4.0 of the NCI Common Terminology Criteria for Adverse Events (CTCAE) which is identified and located on the CTEP website at: http://ctep.cancer.gov/protocolDevelopment/electronic_applications/ctc.htm.

If possible, symptoms should be managed symptomatically. In the case of toxicity, appropriate medical treatment should be used (including anti-emetics, anti-diarrheals, etc.).

All adverse events experienced by participants will be collected from the time of the enrollement, through the study and until the final study visit. Participants continuing to experience toxicity at the off study visit may be contacted for additional assessments until the toxicity has resolved or is deemed irreversible.

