In light of the significant sampling errors in the classification of men considered appropriate for active surveillance, repeat biopsy in follow up has been used as a component of surveillance protocols. Memorial Sloan Kettering Cancer Center adopted a strategy of recommending immediate rebiopsy for all men considering AS at their institution [35]. Between 2002 and 2007, 104 men who met eligibility criteria for AS at Memorial Sloan Kettering Cancer Center (Table 1) underwent immediate 14-core rebiopsy [35]. Among these rebiopsies, 26% had no cancer identified. For those with cancer on the rebiopsy, 77% had Gleason ≤6, 22% had Gleason 7 and one man had Gleason 9. From the standpoint of upstaging of disease extent, 13% were found to have >3 cores positive and 16% had >50% of any core involved. In total, 27% had either upstaging or up-grading on the biopsy. A subset of these men, 64%, had an erMRI prior to re-biopsy with 27% showing a finding concerning for ECE. None of the men without evidence of ECE were up-staged or upgraded compared to 39% among those with concerning MRI features. A subsequent analysis showed that those men without cancer identified on the confirmatory biopsy were less likely to progress to definitive treatment over the course of the study [22]. Other retrospective analyses show similar results [36, 37]. In line with these results, the first biopsy following diagnosis has tended to result in the greatest number of men being upgraded on AS protocols [38, 39]. Though biopsy remains the gold standard for reclassification, it carries what appear to be increasing risks [40, 41]. Highlighting the short-term effects, in one recent report of nearly one thousand men who had undergone biopsy, 44% noted pain, 66% had hematuria, 37% had hematochezia, 93% had hemoejaculate and 18% had fever in the days following the procedure [42]. Many of these symptoms were not considered moderate or serious problems by the participants though 15% had some pain and 3% had fever two weeks or more after the biopsy. Significantly, the rates of hospitalization for infections following prostate biopsies appear to be increasing [40, 43, 44]. Though the absolute rates of sepsis following biopsy remain low [42, 43], the increasing risk appears to be related to resistance to antibiotics used in pre-biopsy prophylaxis [41, 45]. These findings highlight that approaches other than frequent, repeated biopsies will be necessary to classify men as candidates for AS.

Prostate MRI

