8.3 Reporting to the Study Sponsor

8.3.1 Serious Adverse Event Reporting

All serious adverse events that occur after the initial study procedure, or within 30 days of the last study procedure treatment must be reported to the DF/HCC Overall Principal Investigator on the local institutional SAE form. This includes events meeting the criteria outlined in Section 11.1.2, as well as the following:

- Grade 2 (moderate) and Grade 3 (severe) Events Only events that are unexpected and possibly, probably or definitely related/associated with the intervention.
- All Grade 4 (life-threatening or disabling) Events Unless expected AND specifically listed in the protocol as not requiring reporting.
- All Grade 5 (fatal) Events When the participant is enrolled and actively participating in the trial OR when the event occurs within 30 days of the last study intervention.

Note: If the participant is in long term follow up, report the death at the time of continuing review.

Participating investigators must report each serious adverse event to the DF/HCC Overall Principal Investigator within 24 business hours of learning of the occurrence. In the event that the participating investigator does not become aware of the serious adverse event immediately (e.g., participant sought treatment elsewhere), the participating investigator is to report the event within 24 business hours after learning of it and document the time of his or her first awareness of the adverse event. Report serious adverse events by telephone, email or facsimile to:

Within the following 24-48 business hours, the participating investigator must provide follow-up information on the serious adverse event. Follow-up information should describe whether the event has resolved or continues, if and how the event was treated, and whether the participant will continue or discontinue study participation.

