8.6 Monitoring of Adverse Events and Period of Observation

All adverse events, both serious and non-serious, and deaths that are encountered from initiation of study intervention, throughout the study, and within 30 days of the last study intervention should be followed to their resolution, or until the participating investigator assesses them as stable, or the participating investigator determines the event to be irreversible, or the participant is lost to follow-up. The presence and resolution of AEs and SAEs (with dates) should be documented on the appropriate case report form and recorded in the participant's medical record to facilitate source data verification.

For some SAEs, the study sponsor or designee may follow-up by telephone, fax, and/or monitoring visit to obtain additional case details deemed necessary to appropriately evaluate the SAE report (e.g., hospital discharge summary, consultant report, or autopsy report).

Participants should be instructed to report any serious post-study event(s) that might reasonably be related to participation in this study. Participating investigators should notify the DF/HCC Overall Principal Investigator and their respective IRB of any unanticipated death or adverse event occurring after a participant has discontinued or terminated study participation that may reasonably be related to the study.

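### The last scheduled adverse-event assessment can fall before the plan's own 30-day limit after the last study procedure, and no calendar contact covers the days between

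*Combined protocol and SAP*

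**What the plan says.** Section 6 sets the collection period: "All adverse events experienced by participants will be collected from the time of the enrollement, through the study and until the final study visit". Section 5.5 places that endpoint at the "final study visit which will occur up to 60 days after the final biopsy", and the calendar column in section 7 reads "End of Study Visit (within 60 days of final bx"). Neither gives an earliest day. The calendar marks adverse-event evaluation at three points only: the MRI visit, the final biopsy visit and the end-of-study visit.

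Section 8 uses a different clock. Section 8.3.1 requires reporting to the overall principal investigator of "All serious adverse events that occur after the initial study procedure, or within 30 days of the last study procedure treatment". Section 8.6 covers serious and non-serious events "from initiation of study intervention, throughout the study, and within 30 days of the last study intervention". The AE definition in section 8.1.1 also starts at the first treatment or protocol procedure, not at enrollment.

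On leaving the study, section 5 says that every participant comes off after an end-of-study visit timed from the final biopsy. Sections 5 and 5.2.2 take T3/N1 men off protocol after the MRI. Section 5.3.4.2 takes men off study when the TRUS biopsy no longer meets the entry criteria, and section 5.6 repeats this as a removal criterion.

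**The concern.** The plan promises AE observation for at least 30 days after the last procedure, yet its last scheduled look for events can come well before day 30. The protocol's own background gives reason to care about that interval. In the biopsy series it cites, "15% had some pain and 3% had fever two weeks or more after the biopsy", and it describes hospital admission for infection after biopsy as rising. The data and safety monitoring committee reviews toxicity quarterly (section 9.2), so incomplete capture would reach a body that relies on it.

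What is at stake is the completeness of the safety record, mainly for non-serious events that begin after an early final visit. The gap is clearest for men who leave early, because the text does not settle whether or when they have a final AE assessment.

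**Working it through.** The plan states no figure to reproduce. The check sets the rules side by side and then measures the gap.

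**Step 1: the rules.**

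| Section | Scope | Start | End |
|---|---|---|---|
| 6 | AE collection | Enrollment | Final study visit |
| 8.1.1 | AE definition | First treatment or procedure | Not stated |
| 8.3.1 | SAE reporting | Initial procedure | 30 days after last procedure |
| 8.6 | AE and SAE observation, follow-up to resolution | Start of intervention | Through the study and 30 days after last intervention |
| 5.5 and 7 | Visit date only | – | Up to 60 days after biopsy, no minimum |

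There are two end rules: the final visit, and 30 days after the last procedure. Section 5.5 is not a window of its own; it fixes the date that section 6 uses.

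**Step 2: length of the gap.** Let v be the day of the final visit, counted from the biopsy as the last procedure, with v at most 60. Days up to day 30 without a scheduled assessment = max(0, 30 − v).

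- v = 7: 30 − 7 = 23 days
- v = 14: 30 − 14 = 16 days
- v = 30 or later: 0 days

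The documents do not say how visits will be spread over the 60 days, so the share of men with v below 30 could be anywhere from 0 to 100%.

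**Step 3: what would catch an event in the gap.**

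- Section 8.2 ties AE assessment to participant evaluation time points, and the calendar has none after the final visit.
- Section 6 allows, but does not require, further contact, and only for toxicity already present at the off-study visit.
- Section 8.3.1 makes SAEs to day 30 reportable, but creates no contact through which the site would learn of them.
- Section 8.6 asks participants to volunteer serious post-study events.
- The AE form in section 9.1.2 is due by reference to a treatment cycle. This study has none, so the form schedule fixes no closing date.

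A new non-serious event after an early visit therefore has no scheduled capture. A new SAE is reportable, but only if the site hears of it.

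**Step 4: men who leave early.**

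- T3/N1 men: section 11.1 plans 130 enrolled and roughly 10 taken off; 130 − 120 = 10, and 10/130 = 7.7%. Section 5 gives all participants an end-of-study visit, but times it from a biopsy that these men do not have on protocol. Their last clearly scheduled AE assessment is the MRI visit, where they receive gadolinium.
- Men upgraded on TRUS biopsy: section 11.2 assumes 30 of 120. Section 5 keeps them until the end-of-study visit; sections 5.3.4.2 and 5.6 remove them on the biopsy result.

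On these planning figures, the timing of the last AE assessment is unclear for about 10 + 30 = 40 of 130 men, apart from any early final visits among the others.

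**The case against.** The strongest reply is that the sections do different jobs. Section 6 governs routine collection, 8.3.1 SAE reporting and 8.6 observation and follow-up, so collection may stop at the visit while observation runs to day 30. The most serious harm is also the best covered: hospital admission for infection is an SAE, reportable to day 30 even when the site learns of it late. Section 5 gives every participant an end-of-study visit, and section 11 plans no AE analysis. All of this is fair, and it limits the point to capture of events. It does not supply the contact by which observation to day 30 would be carried out, nor date the visit for T3/N1 men.

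Three stronger readings are tempting but not supported:

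- **Days 31 to 60 fall outside section 8.6 for a man seen on day 60.** Section 8.6 covers events throughout the study, and section 5 keeps a man on study until his end-of-study visit, so those days are covered.
- **About 18 men with pain and 3 to 4 with fever would be missed.** The products are 0.15 × 120 = 18 and 0.03 × 120 = 3.6, but the cited rates count men with symptoms at two weeks or later. They do not say when the symptoms began. The same series reports 44% with pain and 18% with fever in the first days, so some of these symptoms may have persisted from then and would be seen at an early visit.
- **Event rates would not be comparable between men.** Observation time can differ, but this is a single-arm accuracy study with no planned comparison of AE rates.

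Nor can late post-biopsy events be the issue for T3/N1 men. Theirs would be events after the MRI and contrast.

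**Conclusion.** The point holds as a gap in safety follow-up and is minor. The final visit that ends section 6 collection has no earliest day, while sections 8.3.1 and 8.6 run to at least 30 days after the last procedure. A visit before day 30 leaves up to 30 − v days without a scheduled assessment. The last assessment is also unclear for roughly 10 T3/N1 men, and, if the plan's 25% upgrade rate holds, for about 30 men upgraded on biopsy.

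The number of events missed cannot be estimated: the documents give neither the spread of visit dates nor the rate of events that first arise after an early visit. The primary analysis of true and false positive fractions and the stated 81% power are unaffected. The start dates differ too (enrollment against first procedure), but the documents show no material consequence beyond collecting events that section 8.1.1 does not define as adverse events.

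**What to change.** Reconcile sections 6, 8.1.1, 8.3.1 and 8.6 to one start and one end. Add a footnote to the AE row of the study calendar: the last AE assessment, by visit or telephone, takes place no earlier than the plan's own 30 days after the last study procedure, for every man, including those who leave after the MRI or after an upgrading biopsy. For T3/N1 men, count from the MRI. Sections 5, 5.3.4.2 and 5.6 should also be reconciled on when an upgraded man comes off study; the footnote works whichever rule is kept.

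The cost is wording in these sections, one footnote, and a short telephone contact for men with an early final visit, for about 10 T3/N1 men, and for any upgraded men who leave before day 30. No extra clinic visit or procedure is needed, and sample size and analysis do not change.
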